Immune-Related AEs	Toxicity Grade or Conditions (CTCAE v5.0)	Action Taken with Pembrolizumab
All other immune-related AEs	Intolerable/persistent Grade 2	Withhold.
	Grade 3	Withhold or discontinue based on the type of event. Events that require discontinuation include, but are not limited to, Guillain-Barre Syndrome and encephalitis.
	Grade 4 or recurrent Grade 3	Permanently discontinue.

AE: adverse event; ALT: alanine aminotransferase; AST: aspartate aminotransferase; CTCAE: Common Terminology Criteria for Adverse Events; GI: gastrointestinal; irAE: immune-related adverse event; IV: intravenous.
^a Withholding or permanently discontinuing pembrolizumab is at the discretion of the investigator or treating physician.

For patients with Grade 3 or 4 immune-related endocrinopathy that does not require withholding of pembrolizumab, pembrolizumab may be resumed when the AE resolves to Grade ≤ 2 and is controlled with hormonal replacement therapy or metabolic control has been achieved (in case of type 1 diabetes mellitus).

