10.3 Monitoring of AEs and Period of Observation

AEs, both nonserious and serious, will be monitored throughout the study as follows:

- AEs will be reported from the signing of informed consent through 30 days after administration of the last dose of study drug or the start of subsequent anticancer therapy, whichever occurs first, and recorded in the eCRFs. The reporting period for irAEs (Section 8.6.3.2) is extended to 90 days after administration of the last dose of study drug or the start of subsequent anticancer therapy, whichever occurs first, and recorded in the eCRFs.
- SAEs will be reported to the Takeda Global Pharmacovigilance department or designee from the signing of informed consent through 30 days after administration of the last dose of study drug, even if the patient starts nonprotocol therapy, and recorded in the eCRF. The reporting period for serious irAEs is extended to 90 days after administration of the last dose of study drug. After this period, only related SAEs must be reported to the Takeda Global Pharmacovigilance department or designee. SAEs should be monitored until they are resolved or are clearly determined to be caused by a patient's stable or chronic condition or intercurrent illness(es).

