13.10 Safety Analysis

The safety and tolerability of modakafusp alfa will be assessed by the recording of TEAEs (NCI CTCAE, Version 5.0), vital signs, chemistry and hematology, urinalysis, ECG, and concomitant medications.

AEs will be coded using the MedDRA. TEAEs that occur after administration of the first dose of study drug and through 30 days after the last dose of study drug will be summarized by MedDRA System Organ Class and PT in the safety analysis set.

13.11 [REDACTED]

[figure not shown]

Table 13.a

The content of Table 13.a is entirely redacted with a solid black fill, making the data and structure of the table unreadable.

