- ^t Patients will be followed for survival every 12±1 weeks until death, loss to follow-up, consent withdrawal, or study termination. Survivor information and death details may be collected by methods that include, but are not limited to, telephone, e-mail, mail, or retrieval from online or other databases (eg, Social Security indexes). In addition, the start of another anticancer therapy for the disease under study will be collected.

16.4 Table 16.d Schedule of Events: Screening, Baseline, Cycle 1, Cycle 2, and Cycle 3 (Phase 2 Dose Expansion)

Table 16.d Schedule of Events: Screening, Baseline, Cycle 1, Cycle 2, and Cycle 3 (Phase 2 Dose Expansion)

Study Period or Treatment Cycle	Screening	Cycle 1						Cycle 2		Cycle 3						
		Day <21	Day 1	Day 2	Day 3	Day 4	Day 8	Day 15	Day 1	Day 2	Day 1	Day 2	Day 3	Day 4	Day 8	Day 15
Window Allowed		0	0	0	0	±2 d	±2 d	±2 d	0	±2 d	±0 d	0	0	±2 d	±2 d	
Informed consent ^a	X															
Eligibility criteria	X															
Demographics	X															
Medical history	X															
Prior medication and treatment history	X															
Height (screening only) and weight	X							X		X						
ECOG performance status	X	X						X		X						
12-lead ECG ^b	X	X						X		X						
Triplicate 12-lead ECG ^b		(X)	(X)													
Physical examination	X	X						X		X						
Vital signs ^c	X	X						X		X						
Monitoring of concomitant medication/procedures	Recorded from signing of the ICF through 30 days after last dose of study drug or the start of subsequent anticancer therapy, whichever occurs first.															
AE reporting	Recorded from signing of the ICF through 30 days after last dose of study drug or the start of subsequent anticancer therapy, whichever occurs first. The reporting period for irAEs is extended to 90 days after administration of the last dose of study drug or the start of subsequent anticancer therapy, whichever occurs first, and recorded in the eCRFs.															
	SAEs will be reported from signing of ICF through 30 days after last dose of study drug even if the patient starts nonprotocol systemic therapy. Serious irAEs will be reported through 90 days after last dose of study drug.															
Dosing																
Modakafusp alfa infusion ^d		X							X		X					
Pembrolizumab infusion ^e		X									X					
Disease Assessment																
CT/MRI scans ^f	X	Repeat every 6 weeks through Cycle 6 then every 9 weeks thereafter.														

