Table 16.d Schedule of Events: Screening, Baseline, Cycle 1, Cycle 2, and Cycle 3 (Phase 2 Dose Expansion)

Study Period or Treatment Cycle	Screening	Cycle 1						Cycle 2		Cycle 3						
		Day ≤21	Day 1	Day 2	Day 3	Day 4	Day 8	Day 15	Day 1	Day 2	Day 1	Day 2	Day 3	Day 4	Day 8	Day 15
Window Allowed		0	0	0	0	±2 d	±2 d	±2 d	0	±2 d	±0 d	0	0	±2 d	±2 d	
Laboratory Assessments																
Chemistry ^e	X	(X)				X	X	X		X				X	X	
Blood type ^v	X															
Hematology ^h	X	(X)				X	X	X		X				X	X	
Urinalysis ^l	X	X						X		X						
Pregnancy test ^k	(X)	(X)						(X)		(X)						
Immunosafety markers ^l	X									X						
Tumor biopsy ^m	(X)								(X) ^x	(X) ^y						
Serum sample for modakafusp alfa PK ⁿ	Please refer to Table 16.g and Table 16.h below.															
Pembrolizumab PK ⁿ	Please refer to Table 16.g and Table 16.h below.															
Blood sample for immunophenotyping ^o		X ^p	X	X		X		X ^p	(X) ^x	X ^p	X	X		X		
Blood sample for receptor occupancy		X ^q	X	X		X				X ^q	X	X				
Serum sample for circulating biomarkers ^d		X ^q	X	X		X		X ^q	(X) ^x	X ^q	X	X		X		
Serum sample for immunogenicity (ADA) ^{d,r}		X						X		X						
Blood sample for DNA ^s	X															
Blood sample for RNA		X ^p	X	X				X ^p	(X) ^x	X ^p	X	X				
Blood sample for receptor sequencing		X ^p				X		X ^p		X ^p						
Blood sample for circulating tumor cells ^w		X ^p														
Plasma for cfDNA		X ^p														

Footnotes are on the last page of the SOE.

CONFIDENTIAL

16.5 Table 16.e Schedule of Events, Continued: Cycle 4 Through EOT and Follow-up (Phase 2 Dose Expansion)

Table 16.e Schedule of Events, Continued: Cycle 4 Through EOT and Follow-up (Phase 2 Dose Expansion)

Study Period or Treatment Cycle	Cycles 4, 5, 6, 8, 9, 10, 11, 12, 13, 14, and 16+	Cycle 7 and Cycle 15		EOT	Follow-up	
		Day 1	Day 2		PFS ^f	OS ^g
Day	Day 1	Day 1	Day 2	30 (+10) Days After Last Dose or Before Start of Subsequent Systemic Anticancer Therapy, Whichever Occurs First	Q12W	
Window Allowed	±4 d	±4 d	0		±1 week	
Weight	X	X				
ECOG performance status	X	X				
12-lead ECG ^b				X		
Directed physical examination	X	X				
Vital signs ^c	X	X				

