- ^r Blood samples for immunogenicity (ADA) testing will be collected before the dose on Day 1 of every cycle while the patient remains in treatment and, if possible, at the EOT follow-up visit. In case of an IRR, blood draws should be performed for central evaluation of immunogenicity.
- ^s One blood sample for DNA will be taken at either screening or C1D1 predose (when it is not possible to collect at screening, samples can be collected at the next visit).
- ^t Patients who discontinue modakafusp alfa for reasons other than PD will continue PFS follow-up every 12±1 weeks from the EOT visit until the occurrence of PD, death, the start of subsequent systemic anticancer therapy, study termination, or until 6 months after the discontinuation of study treatment, whichever occurs first. PFS will be assessed according to RECIST v1.1.
- ^u Patients will be followed for survival every 12±1 weeks until death, loss to follow-up, consent withdrawal, or study termination. Survivor information and death details may be collected by methods that include, but are not limited to, telephone, e-mail, mail, or retrieval from online or other databases (eg, Social Security indexes). In addition, the start of another anticancer therapy for the disease under study will be collected.
- ^v A sample for blood typing to be taken only at screening. Blood banks need to be alerted that the patient is going to receive an anti-CD38 antibody that may interfere with blood typing in a manner similar to daratumumab. If the blood bank issues a compatibility card, it should be made available to the patient. The patient needs to tell other healthcare providers that he/she is receiving an anti-CD38 antibody if, for example, a blood transfusion is needed.
- ^w A whole blood sample will be collected to quantify CTCs at baseline and correlate with response.

- ^x Pharmacodynamic samples to be collected for patients enrolled within the safety lead-in and those enrolled within the expansion cohorts prior to futility being met.
- ^y After futility has been met within an expansion cohort, the on-treatment biopsy sample should be taken prior to Cycle 3 administration of modakafusp alfa and pembrolizumab. For convenience, biopsy can be taken up to a 7 days prior to C3D1, preferably to coincide with imaging assessments of disease.

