7.12 Safety Analysis

7.12.1 Adverse Events

Adverse events will be coded using the Medical Dictionary for Regulatory Activities (MedDRA) Version 23.0 or later (based on version at time of database lock). Treatment-emergent is defined as any AE that occurs on or after the date of the first dose of any study treatment through 30 days after the last dose of any study treatment.

Treatment-emergent AEs will be summarized by MedDRA system organ class (SOC), and preferred term. For summary tabulations the following hematologic abnormalities coded to MedDRA preferred terms in the Investigations SOC will be pooled with the appropriate clinical terms in the blood and lymphatic system disorders SOC:

MedDRA Preferred Term (Investigation SOC)	Mapped to (Blood and lymphatic system disorders SOC)
Neutrophil count decreased	Neutropenia
Platelet count decreased	Thrombocytopenia
Hemoglobin decreased	Anemia
White blood cell count decreased	Leukopenia

Treatment-emergent AEs will also be summarized by the National Cancer Institute Common Terminology Criteria for Adverse Events (NCI CTCAE) version 5.0.

Summary tabulations will include the following categories:

- Treatment-emergent AEs.
- Drug-related treatment-emergent AEs.
- Grade 3 or higher treatment-emergent AEs.
- Grade 3 or higher drug-related treatment-emergent AEs.
- Grade 3 and Grade 4 TEAEs (based on maximum severity).
- Grade 3 and Grade 4 drug-related TEAEs (based on maximum severity).
- The most commonly reported treatment-emergent AEs (i.e., those events reported by $\geq 10\%$ of all patients in each phase or overall population as appropriate).
- Serious treatment-emergent AEs.
- Drug-related serious treatment-emergent AEs.
- Treatment-emergent AEs resulting in discontinuation of study drug.
- Treatment-emergent AEs resulting in study drug modifications (including discontinuation, delay, reduction, and interruption).

- Treatment-emergent AEs resulting in dose delays.
- Treatment-emergent AEs resulting in dose reductions.
- Treatment-emergent AEs resulting in dose interruptions.
- TEAEs leading to death
- Treatment emergent AESI – all grades
- Treatment emergent AESI grade 3 and above
- Treatment emergent AESI grade 3 or 4
- Treatment-emergent AEs resulting in infusion rate reductions.
- Treatment-emergent AEs resulting in infusion interruptions.
- Serious treatment emergent AESI

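### irAEs are collected to 90 days after last dose but AEs are tabulated only to 30 days, so a late-onset irAE enters no planned AE, SAE or AESI incidence table unless it is a related death

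*SAP*

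**What the plan says.** **Collection.** Protocol 10.3 stops general AE reporting 30 days after the last dose, then makes an exception: "The reporting period for irAEs (Section 8.6.3.2) is extended to 90 days after administration of the last dose of study drug". For non-serious irAEs this ends early if subsequent anticancer therapy starts first. For serious ones the text is "The reporting period for serious irAEs is extended to 90 days after administration of the last dose of study drug", with no stop at subsequent therapy. The phase 2 schedule in Appendix A agrees: "Serious irAEs will be reported through 90 days after last dose of study drug".

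**Analysis.** SAP 7.12.1 takes as treatment-emergent "any AE that occurs on or after the date of the first dose of any study treatment through 30 days after the last dose", counted from the last dose of any study treatment. Protocol 13.10 likewise plans that events "through 30 days after the last dose of study drug will be summarized by MedDRA System Organ Class and PT". Neither makes an exception for irAEs.

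**Outputs.** All the AE, SAE and AESI tabulations named in SAP 7.12.1 are labelled treatment-emergent. The AE and SAE rows of the overall summary are subsets of TEAEs, and the disclosure table of frequent non-serious events is also TEAE-based. The on-study deaths row looks past day 30, but only for deaths judged related. In SAP Appendix A the AE listings are confined to TEAEs or Cycle 1 DLTs, apart from Serious AEs and the death listings.

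**The concern.** Protocol 4.3.5 says that known PD-1 immune toxicities may be enhanced when modakafusp alfa is added, and this is the one class of event for which the protocol lengthens general AE collection. The analysis does not follow. The pembrolizumab AESI list is largely immune-mediated, yet its tables stop at day 30 like all the others.

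The effect has one direction. A 30-day cut can remove collected late irAEs from the tables but cannot add any, so the reported incidence of the combination's stated risk can only be too low. A reader of the clinical study report would see a complete-looking AESI table with no sign that later events had been collected and left out.

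**Working it through.** There is no stated figure to reproduce. The check compares the windows, traces each kind of late event through the planned outputs, and then asks for whom the gap is shorter. The redacted sections (protocol 13.11, SAP 7.13) were not relied on.

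**1. Windows, taking one common last dose.** Collected to day 90 and tabulated to day 30: 90 − 30 = 60 days, or 60/90 = two thirds of the post-treatment irAE window.

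| irAE onset (days after last dose) | Collected under 10.3 | Treatment-emergent under SAP 7.12.1 |
|---|---|---|
| 30 | yes | yes |
| 31, 60, 90 | yes | no |
| 91 | only if a related SAE | no |

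**2. Where an irAE starting after day 30 can appear.**

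| Late irAE | AE, SAE and AESI incidence tables | Elsewhere |
|---|---|---|
| Non-serious | none | no AE listing; related laboratory values may be listed under SAP 7.12.2 |
| Serious, not fatal | none | Serious AEs listing |
| Fatal and judged related | on-study deaths row only | Serious AEs and death listings |

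**3. Patients with a shorter gap.**
- *Non-serious irAE, subsequent therapy starting on day S.* Gap = max(0, min(90, S) − 30). It is zero if S is 30 or less.
- *Pembrolizumab continued alone.* Protocol 10.3 counts from the last dose of *study drug*; the SAP counts from the last dose of *any study treatment*. Protocol 8.6.4 lets a patient stop modakafusp alfa and stay on pembrolizumab, and 8.6.4.1 uses *study drug* under the modakafusp alfa heading. If that is also its meaning in 10.3, and the last pembrolizumab dose comes L days after the last modakafusp alfa dose, the gap = max(0, 90 − (L + 30)) = max(0, 60 − L). One six-week interval (L = 42) leaves 18 days; L of 60 or more leaves none.

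**4. Scale.** One patient is 1/25 = 4.0 percentage points in a full cohort, unless already counted for that term. The documents give no late-onset rate. Purely as an assumption, if 1% to 5% of at-risk patients had a first irAE on days 31 to 90:
- all 84 phase 2 patients at risk: 84 × 0.01 = 0.84 to 84 × 0.05 = 4.2 patients;
- half at risk (a second assumption): 42 × 0.01 = 0.42 to 42 × 0.05 = 2.1 patients.

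**5. How complete the late data will be.** Table 16.e sets EOT at "30 (+10) Days After Last Dose or Before Start of Subsequent Systemic Anticancer Therapy, Whichever Occurs First", so normally days 30 to 40. Patients stopping for reasons other than PD "will continue PFS follow-up every 12±1 weeks from the EOT visit". Since 12 ± 1 weeks is 77 to 91 days, the first such visit falls between day 30 + 77 = 107 and day 40 + 91 = 131, after the 90-day window has closed. This timing applies only to patients entering PFS follow-up after an EOT on days 30 to 40. Survival follow-up after PD is also 12-weekly, but its start is not tied to EOT.

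**6. Date imputation.** Under SAP Appendix B, an onset with a missing day in a later month than first dose is set to the first of that month. This could pull an occasional late event inside 30 days but does not close the gap.

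**The case against.** The strongest reply is that nothing promised is broken. No objective or endpoint names irAEs, the TEAE tables match the TEAE endpoints, and collecting for longer than one tabulates is not in itself a contradiction: 10.3 also takes in related SAEs with no end date. This stands. It is why the 30-day definition should be kept and the remedy is an addition.

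A reader might infer that late irAEs vanish. The documents do not support that. Serious ones can be listed, related deaths are counted, and SAP 7.12.2 lists unscheduled laboratory results and sets no stated 30-day limit on its shift tables; TSH, free T4 and cortisol are also taken at EOT. But a listing gives no incidence, and laboratory values do not replace a graded AE.

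A reader might also infer that the SAE-count endpoints are left undelivered, because their wording carries no treatment-emergent limit while the SAE tables do. That over-reads silence. Taken literally, the wording would also admit SAEs between consent and first dose and related SAEs after day 90, and protocol Table 6.a defines the endpoint only as standard safety assessments. One clarifying line is enough.

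Two practical objections also stand. Few late events may be captured, which calls for a footnote but is no reason to leave out those reported. And no irAE flag is described: the documented causality question is only related or not, and Table 8.c ends in a catch-all, "All other immune-related AEs", which cannot be programmed from its wording. An investigator flag might therefore be new data collection.

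**Conclusion.** The point holds. On the text as written, an irAE that starts after the 30-day window but within the 10.3 collection window is counted in no planned AE, SAE or AESI incidence table, the sole exception being a related death in the on-study deaths row. The clearest loss is the non-serious late irAE, which has no AE output at all.

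The size cannot be determined from the documents; the figures under assumed rates show scale only and the conclusion does not rest on them. The direction is certain: towards understating irAE incidence. A uniform 60-day gap for every patient is not established, because subsequent therapy shortens it for non-serious events and the choice of clock may shorten or remove it for patients continuing pembrolizumab alone. No DLT assessment, dose choice or stopping decision is claimed to depend on these events. It is a reporting omission that is cheap to correct before database lock.

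**What to change.** Keep the 30-day TEAE definition in SAP 7.12.1 and protocol 13.10. In SAP 7.12.1 add, for combination-treated patients:

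- one supplementary incidence table, by preferred term and grade, and one listing of immune-mediated events through the end of the 10.3 collection window, flagging onset more than 30 days after last dose;
- an identification rule using data already collected: the pembrolizumab AESI terms excluding IRR, the named Table 8.c categories, and any event entered under the extended irAE reporting period. Use an investigator flag only if the eCRF already has one. Late serious events outside the named categories need a stated rule, because 10.3 also admits related SAEs that are not immune-mediated;
- a statement of which drug's last dose starts the collection window and which starts the TEAE window;
- one line saying whether the SAE-count endpoints are treatment-emergent only;
- a footnote that late counts may be incomplete, because no safety visit is scheduled between EOT and the 12-weekly follow-up.

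The cost is one table, one listing and a footnote, plus a few sentences of definition. No new data are needed if the identification rule stays within existing fields. Reported irAE counts may look slightly less favourable, and the late ones will rest largely on unscheduled or retrospective reporting.

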4.3.5 Potential Overlapping Toxicities

Nonclinical toxicology studies evaluating the combination of modakafusp alfa and pembrolizumab were not conducted and are not warranted per ICH S9 ([ICH 2018](#)). Pembrolizumab is a mAb that binds to the human PD-1 receptor and blocks the interaction of PD-1 with PD-L1/PD-L2.

Modakafusp alfa and pembrolizumab both activate the immune system, so known PD-1 immunotherapy-related toxicities (eg, pneumonitis, colitis, hepatitis, dermatitis, IRRs, endocrinopathies, and nephritis) observed following the administration of pembrolizumab may be enhanced when combined with modakafusp alfa. Details regarding the full safety profile of pembrolizumab can be found in the FDA-approved package insert ([Keytruda \(pembrolizumab\) PI 2018](#)). To minimize the risk to patients treated with modakafusp alfa and pembrolizumab, phase 2 will include a safety lead-in phase for the combination cohorts to determine the safety and tolerability of the combination doses and regimen. Pembrolizumab will be administered at the approved dose and schedule of 400 mg IV once every 6 weeks (Q6W) to maximize the possibility of observing clinical benefit.

The safety of the pembrolizumab and pegylated interferon alfa-2b (PEG-IFN) combination was studied in 2 phase 1/2 studies. Seventeen patients were enrolled in the Keynote-029 trial ([Atkins et al. 2018](#)), 5 with melanoma and 9 with renal cell carcinoma (RCC). Across dose levels, the most common treatment-related AEs of any grade were fatigue (n = 11, 65%), pyrexia (n = 7, 41%), chills, diarrhea and nausea (n = 6, 35% each). Grade 3 to 4 AEs were fatigue (n = 1), AST increase (n = 1), neutropenia (n = 1), and depression (n = 2). Forty-three patients with melanoma were enrolled in the Keynote-020 trial ([Davar et al. 2018](#)). The most frequent treatment-related toxicities were Grade 1 hyponatremia (11.1%), Grade 2 lymphopenia (10.8%), Grade 3 hyponatremia (10.3%), Grade 3 lymphopenia (12%) and Grade 3 fatigue (16.2%). Fifteen patients (34.9%) developed immune-related AEs (irAE) of any grade, including vitiligo (16.3%), hypothyroidism (16.3%), and one patient each with adrenal insufficiency (Grade 3), pneumonitis (Grade 4), and uveitis (Grade 4). No treatment-related deaths occurred.

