8.6.3.1 Modakafusp Alfa Dose Modification Guidelines

[Table 8.b](#) provides general dose modification recommendations for modakafusp alfa. When the dose of modakafusp alfa is withheld on the basis of these criteria, clinical and laboratory re-evaluation should be repeated at least weekly or more frequently, depending on the nature of the toxicity observed, until the toxicity resolves to Grade ≤ 1 or baseline. If there are transient laboratory abnormalities that, based on investigator assessment, are not clinically significant, continuation of therapy without dose modification is permissible upon discussion with the sponsor. See details for managing specific AEs in [Section 8.10](#).

Table 8.b Dose Modification Recommendations for Toxicities Possibly Related to Modakafusp Alfa

Criteria	Action
Grade 1 AEs	No dose reductions or interruptions.
Grade 2 AEs	Patients experiencing Grade 2 AEs considered related to study treatment that are not easily managed or corrected and are not tolerable to the patient, or AEs that are not acceptable in the investigator's judgment, should have study treatment interrupted until the AE resolves to Grade ≤ 1 or baseline and then restarted at the same dose or, depending on the toxicity, at the previous safe dose level or below.
Grade 3, Grade 4 (not life-threatening per seriousness criteria), and Grade 4 asymptomatic laboratory AEs	Hold modakafusp alfa until resolution to Grade ≤ 1 or baseline, and then resume treatment at a reduced dose level. In case of Grade 3 hematological toxicity (anemia, thrombocytopenia, neutropenia, or lymphopenia) or Grade 3 asymptomatic laboratory AEs, the patient can continue at the same dose or a reduced dose at the investigator's discretion.
Grade 4 (life-threatening per seriousness criteria) AEs	Permanently withdraw the patient from the study.
AEs of all grades	If treatment has been held for >14 consecutive days without resolution of the toxicity (to baseline or Grade ≤ 1), consider permanently discontinuing study treatment unless there is clinical benefit for the patient as assessed by the investigator and with sponsor's approval. Treatment can be resumed at a reduced dose level after resolution of AEs to Grade ≤ 1 or baseline.

AE: adverse event.

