All summaries will be by dose levels by phases (escalation, safety lead-in, and expansion) for patients in the safety analysis set.

Patients with the same AE more than once will have that event counted only once within each body system, and once within each preferred term. Patients with the same AE more than once will have the maximum intensity of that event counted once within each body system, and once within each preferred term.

Most commonly reported (at least 10% of all patients in each phase or overall population as appropriate) treatment-emergent AEs will be presented by preferred term only. Patients with the same AE more than once will have that event counted only once within each preferred term.

An overall summary TEAE table will include numbers and percentages of patients who had any TEAE, and qualified TEAEs: drug-related AE, not drug-related AE, grade 3 or higher TEAE, grade 3 or higher drug-related AE, serious AE (SAE), drug-related SAE, not drug-related SAE, SAEs leading to study drug discontinuation, AEs resulting in study drug discontinuation, and on-study deaths. On-study death is defined as deaths that occur between the first dose of study drug and up to 30 days after the last dose of study drug and deaths assessed related to study drug that occur 30 days after the last dose of study drug.

Most frequent, >5% of all patients in each phase or overall population as appropriate, non-serious TEAE will be presented by system organ class and preferred terms for clinical trial disclosure.

A by-patient listing of DLTs that occur during Cycle 1 of treatment will be presented by dose levels for all patients in the DLT evaluable set. Patients will be grouped by the dose level to which they were originally assigned, including those who receive subsequent treatment at a lower or higher dose level.

A by-patient listing of all deaths regardless of whether on study or not will also be presented. In this listing, on-study deaths will be flagged.

Adverse Events of Special Interest (AESI)

For modakafusp alfa, infusion-related reactions (IRRs) are designated as AESIs.

For pembrolizumab, the following AEs are considered AESIs:

- Pneumonitis.
- Hepatitis.
- Colitis.
- Nephritis.
- Dermatologic reactions.
- Myocarditis.
- IRR.
- Endocrinopathies, including thyroid disorders, adrenal insufficiency, type 1 diabetes mellitus, and hypophysitis.

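### The SAP's pooling table for blood-count terms leaves out lymphopenia, so its incidence by preferred term may be fragmented; a minor, one-row correction

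*SAP*

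**What the plan says.** SAP 7.12.1 sets the unit of tabulation: "Treatment-emergent AEs will be summarized by MedDRA system organ class (SOC), and preferred term". It then states that "the following hematologic abnormalities coded to MedDRA preferred terms in the Investigations SOC will be pooled with the appropriate clinical terms" of the blood and lymphatic class. The table that follows has four rows, for decreased neutrophil count, platelet count, hemoglobin and, last, "White blood cell count decreased", which maps to leukopenia. No row concerns lymphocytes, and no reason is given.

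Two summaries in the same section apply a cut-off to each preferred term. Common events, at 10% or more of patients, are handled so that "treatment-emergent AEs will be presented by preferred term only". The disclosure table covers "Most frequent, >5% of all patients in each phase or overall population as appropriate, non-serious TEAE", by system organ class and preferred term. In both kinds of count a patient contributes once per preferred term.

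Protocol Table 8.b (section 8.6.3.1) gives the sponsor's own list of hematological toxicities: "In case of Grade 3 hematological toxicity (anemia, thrombocytopenia, neutropenia, or lymphopenia". Protocol 4.3.5 cites a study of pembrolizumab plus pegylated interferon in melanoma with Grade 2 lymphopenia at 10.8% and Grade 3 lymphopenia at 12%.

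**The concern.** Of the four toxicities named in Table 8.b, the SAP pools three and omits lymphopenia. It does pool leukopenia, which Table 8.b does not name. Protocol 4.3.3 already reports neutropenia and thrombocytopenia with the count-decreased terms included, so combining the two kinds of term is the sponsor's practice in this study.

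The frequency and severity of TEAEs is a primary endpoint in phase 1b and the safety lead-in and a secondary one in the expansion. If some lymphocyte falls are coded as a laboratory finding and others as a clinical disorder, each row shows only part of the incidence. The lymphopenia row would then not be comparable with the pooled neutropenia and thrombocytopenia rows beside it. Adding the two rows does not repair this: a patient with both terms would be counted twice, so the patient-level rate cannot be read from the table.

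**Working it through.** The plan states no figure on this point, so there is nothing to reproduce. The check has two parts.

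**1. The lists side by side**

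| Toxicity | Named in protocol Table 8.b | Pooled in SAP 7.12.1 |
|---|---|---|
| Anemia | yes | yes |
| Thrombocytopenia | yes | yes |
| Neutropenia | yes | yes |
| Lymphopenia | yes | no |
| Leukopenia | no | yes |

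**2. How many affected patients could fall below a cut-off**

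Inputs: about 30 patients in phase 1b (protocol 13.1.1); 3 × 25 = 75 in the expansion (protocol 13.1.2); cut-offs of at least 10% and more than 5% (SAP 7.12.1). Assumptions: each affected patient carries exactly one of the two terms, and the terms are used equally often.

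If a term needs *k* patients to be shown, the largest number affected with neither term shown is 2 × (*k* − 1).

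- Phase 1b, 10% cut-off: 0.10 × 30 = 3, so *k* = 3; 2 + 2 = 4 patients; 4/30 = 13.3%.
- Expansion, 10% cut-off: 0.10 × 75 = 7.5, so *k* = 8; 7 + 7 = 14 patients; 14/75 = 18.7%.
- Phase 1b, 5% cut-off: 0.05 × 30 = 1.5, so *k* = 2; 1 + 1 = 2 patients; 2/30 = 6.7%.
- Expansion, 5% cut-off: 0.05 × 75 = 3.75, so *k* = 4; 3 + 3 = 6 patients; 6/75 = 8.0%.

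These are upper bounds. The 5% figures refer to non-serious events only, as that table does.

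**3. How likely a miss is, under an assumed rate**

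The documents give no lymphopenia rate for this trial. As an illustration, take 12%, the Grade 3 figure from the cited combination study. The chance that a term with rate *p* reaches *k* patients is the binomial tail P(X ≥ *k*), X ~ Bin(N, *p*). The commoner term has rate 12% × its share: 6% at 50:50, 8.4% at 70:30 and 10.8% at 90:10. For all of phase 2, N = 75 + 9 = 84, with *k* = 9 for the 10% table and *k* = 5 for the 5% table.

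| Table | Pooled | Commoner term, 50:50 | 70:30 | 90:10 |
|---|---|---|---|---|
| ≥10%, N = 84 | 0.69 | 0.065 | 0.27 | 0.56 |
| >5%, N = 84 | 0.98 | 0.57 | 0.84 | 0.96 |
| ≥10%, N = 30 | 0.72 | 0.27 | 0.47 | 0.64 |

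Each unpooled entry is for one term. At 50:50 the other term has the same chance, so the probability that at least one reaches the 10% table is no more than 2 × 0.065 = 0.13 at N = 84 and 2 × 0.268 = 0.54 at N = 30.

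With a higher rate the loss shrinks. At 10.8% + 12% = 22.8%, which assumes that the two cited grades are different patients, the chance for the 10% table at N = 84 is 0.999 pooled, against 0.63, 0.94 and 0.99 for the commoner term at the three splits.

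**The case against.** The strongest reply is that lymphocyte falls are measured elsewhere. SAP 7.12.2 includes lymphocytes in the white-cell differential, assigns CTCAE grades where available, and builds tables of shifts from baseline to worst value. None of this depends on how an adverse event is coded. Under protocol 10.1.2 an abnormal laboratory value becomes an adverse event only if it prompts action or is judged clinically significant, so the laboratory tables are the fuller measure. This stands, and it is the main reason why the point is minor. It does not remove the point: the laboratory tables do not carry relatedness, seriousness or action taken, and the individual profiles and mean-over-time outputs cover only platelets and neutrophils.

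A reader might infer that lymphopenia *is* split and under-reported throughout the safety results. The documents do not support that:

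- They give no reported terms and no coding split. If all sites use one kind of term, nothing changes. The separate count-decreased term for lymphocytes is itself inferred by analogy with the four listed pairs.
- Both terms remain in the full tables by system organ class and preferred term and in the listings. Totals such as any TEAE or any Grade 3 or higher TEAE do not change.
- Mixed use of terms need not dilute the larger row. If every affected patient has the clinical term and some also have the laboratory term, the larger row equals the true rate.

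A reader might also take lymphopenia to be an established toxicity of this drug. Protocol 4.3.3 describes thrombocytopenia and neutropenia among the first 17 patients and mentions no lymphopenia. The early falls in monkeys were slight, not dose related and mostly within the reference range, and lymphocytes rose later (protocol 4.1.2.1). The 10.8% and 12% belong to a different interferon product. What remains is that the sponsor's own dose-modification table names lymphopenia and the pooling table does not.

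Finally, no dose-escalation or response rule uses the lymphopenia count by preferred term, and lymphopenia is not listed as an adverse event of special interest. That also stands.

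**Conclusion.** The omission is a fact of the text and is inconsistent with protocol Table 8.b. Its effect is conditional: if sites use both kinds of term, lymphopenia incidence by preferred term may be fragmented and understated, and it could miss the common-event and disclosure tables. The bounds of 13.3% in phase 1b and 18.7% in the expansion rest on an even split with no patient carrying both terms; they are not expected values. The probabilities rest further on a 12% rate borrowed from another combination. A claim that lymphopenia will be understated in every table goes beyond the documents. Severity is minor: no event is lost, patient-level totals hold, and the laboratory analyses cover the same toxicity. The correction is still worth making before database lock, because pooling decided after the data are seen would be open to question.

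**What to change.** Add one row to the mapping table in SAP 7.12.1: *Lymphocyte count decreased* mapped to *Lymphopenia*. Apply it in every summary that uses the pooling, including the all-TEAE, drug-related, Grade 3 or higher, common-event and disclosure tables. If the omission is deliberate, state the reason there instead.

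The cost is one line in the SAP and one line of code, with no new data. The downside is that the reported lymphopenia rate may be higher than it would be under the present table.
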